#### 9.5.1.1 Sensitivity Analyses of Co-primary Endpoints

To evaluate the robustness of the analysis results, sensitivity analyses will be performed as follows:

- Multiple imputation assuming MAR to handle missing primary variables
  - It will be assumed that the missing percent change values will be normally distributed with a mean 0 and a variance-covariance matrix the same as the observed variance-covariance matrix from subjects in the placebo group and have missing endpoint data.
  - If there are at least 25 subjects **in each treatment group** who discontinue IP but have non-missing endpoint data, an additional multiple imputation will be carried out utilizing the information from these subjects to impute the missing data for subjects **who discontinue IP** and have missing endpoint data.
- **An additional sensitivity analysis will be performed to evaluate the impact of COVID-related out of window visits. Primary analysis will be repeated using FAS. The subjects meeting protocol deviation code 953 (out-of-window visit) will use the analysis window defined in [Table 12-2](#) and the remaining subjects will use the analysis window defined in [Table 12-1](#) (ie, same visit window as the primary analysis).**

#### Supplementary analysis

- In addition to the sensitivity analysis, the primary analysis will be repeated using the CAS (described in Section 6.7) acknowledging there are limitations and biases with this analysis. A non-parametric analysis may also be performed if the assumption of normality is violated.

#### 9.5.1.2 Covariate and Subgroup Analyses of Co-primary Endpoints

In addition to the primary analysis, covariate-adjusted analyses of the co-primary efficacy estimands will be performed as supportive analyses using the baseline covariates in [Section 4.2](#), one at a time, in the primary model used in the primary analyses as appropriate.

Subgroup analyses on the co-primary efficacy estimands will be conducted using the subgroups specified in [Section 4.2](#). Treatment effect differences among subgroups, which represent subgroup by treatment interactions, will be estimated and tested based on statistics from the subgroup repeated measures models.

For covariate and subgroup analyses, the stratification factor from the eCRF will be used. Differences in stratum assignment between data collection via IVRS and eCRF will be tabulated.

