The rationale for the study design and study population is to investigate the effect of evolocumab on LDL across different levels of cardiovascular risk and baseline LDL levels. The 2007 China Guideline on Prevention and Treatment of Dyslipidemia in Adults categorizes patients as high risk if they have coronary heart disease or coronary heart disease equivalent (documented atherosclerosis other than in the coronary arteries, diabetes mellitus or multiple cardiovascular risk factors). The target LDL levels for these patients is < 80mg/dL for those with a history of acute coronary syndrome or both documented atherosclerosis and diabetes mellitus. The target LDL for other high risk subjects was < 100mg/dL. However since the release of subsequent international guidelines in 2007 the target for the latter high risk patients has in practice been moving lower. Patients without very high or high risk features but receiving optimal stable background statin therapy in China are generally of moderate risk for which the 2007 guidelines recommend a target LDL of < 130 mg/dL. For these reasons the recruitment criteria for this trial is based on level of risk with high and very high risk subjects requiring an LDL at screening of at least 80mg/dL on optimal stable background statin therapy and the subjects without high risk features requiring an LDL of at least 130 mg/dL.

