10.1.3 Covariates and Sub-groups

Baseline covariates and sub-groups include, but are not limited to:

- Stratification factors:
 - entry CV risk (high/very high CV risk vs not high/very high CV risk).
- Age: < 65 year, ≥ 65 years
- Sex

- Medical history of Diabetes (yes/no)
- Study baseline LDL-C: < median / \geq median
- Family history of premature coronary heart disease (yes/no)
- Baseline PCSK9
- Diagnosis of HeFH according to protocol defined criteria

Missing data will not be imputed for safety endpoints.

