###### Subgroup by baseline characteristics

- Age (< 65 years,  $\geq$  65 years)
- Sex (female, male)
- Medical history of Diabetes Mellitus (yes/no)
- Baseline LDL-C (< median,  $\geq$  median)
- Family history of premature CHD (yes, no)
- Baseline PCSK9: (< median,  $\geq$  median)
- Body Mass Index (BMI; < 25 kg/m^2, 25 - < 30 kg/m^2,  $\geq$  30 kg/m^2)
- Hypertension (yes, no)
- Current smoker (yes, no)
- Baseline CHD risk factors  $\geq$  2 (yes, no)
- Baseline triglycerides (< median,  $\geq$  median)
- Diagnosis of HeFH according to protocol defined criteria (yes/no)

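### The protocol gives the effect across baseline LDL-C levels as a design rationale, but the SAP tests effect modification by baseline LDL-C only on a median split; a supportive continuous analysis should be added.

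*SAP*

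**What the plan says.** Protocol 2.3 says that the design and population were chosen to "investigate the effect of evolocumab on LDL across different levels of cardiovascular risk and baseline LDL levels". It then derives the entry criteria from fixed LDL-C levels. At screening the floor is 80 mg/dL for high or very high risk subjects and 130 mg/dL for the others; no upper limit is set.

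Protocol 10.1.3 lists the baseline LDL-C subgroup as "Study baseline LDL-C: < median" versus at or above it. SAP 4.2 repeats this cut ("Baseline LDL-C (< median") and cuts two further biomarkers in the same way ("Baseline PCSK9: (< median" and "Baseline triglycerides (< median"). The protocol list gives no cut for PCSK9, does not mention triglycerides, and is expressly open-ended.

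SAP 9.5.1.2 then plans two things for the co-primary endpoints:

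- Subgroup analysis: "Treatment effect differences among subgroups, which represent subgroup by treatment interactions, will be estimated and tested based on statistics from" the subgroup repeated-measures models.
- Adjusted analysis: the variables of SAP 4.2 also serve as covariates in supportive models, entered "one at a time, in the primary model used in the primary analyses as appropriate". No treatment-by-covariate term is mentioned, so this analysis does not address effect modification.

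SAP 9.1 analyses Q2W and QM separately, so each interaction test rests on 150 versus 75 randomized subjects. SAP 5.2 already derives baseline LDL-C as a continuous value, the mean of the two most recent central-laboratory results up to Study Day 1.

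**The concern.** A comparison of two halves cannot show how the treatment effect changes along the LDL-C range, which is what the rationale in Protocol 2.3 asks. The sample median is known only after enrolment and corresponds to none of the fixed levels from which the protocol argues. A clinician reading the result therefore has no LDL-C value to which it applies.

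A split also tests a gradual trend less efficiently than the continuous value does. With about 200 evaluable subjects per dose frequency, an interaction test is weak to begin with. What is at stake is the reading of a supportive result: a non-significant split is thinner evidence of a uniform effect than the same data could give.

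**Working it through.** **Inputs.** From SAP 3.2 (and Protocol 10.2): 150 versus 75 per dose frequency, SD 25, treatment effect 40, dropout 10%. From SAP 9.1: two-sided 0.05. Evaluable numbers are 150 × 0.9 = 135 and 75 × 0.9 = 67.5. Assumed, because the documents give neither: the slope b (percentage points of treatment effect per SD of baseline LDL-C) and the shape of the baseline distribution.

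**The plan's own figure.** The standard error of the treatment difference is 25 × √(1/135 + 1/67.5) = 3.73. Then 40 / 3.73 = 10.7 standard errors, and power per endpoint exceeds 99.99%. The stated 99% per endpoint, and at least 98% for the pair, hold as lower bounds. The documents give no power figure for any interaction.

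**Standard errors of the interaction.**

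- Continuous, per SD of baseline: 25 × √(1/135 + 1/67.5) = 3.73.
- Median split: 25 × √(2/67.5 + 2/33.75) = 7.45.

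**Expected split difference under a linear trend.** This is k × b, where k is the distance between the upper-half and lower-half means in SD units. The share of information kept is (k × 3.73 / 7.45)² = (k/2)².

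| Baseline shape | k | Kept | Lost |
|---|---|---|---|
| Uniform | 1.732 | 75.0% | 25.0% |
| Normal | 1.596 | 63.7% | 36.3% |
| Exponential | 1.386 | 48.0% | 52.0% |

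Simulated shapes extend the picture. Illustrative mixtures using the 80 and 130 mg/dL floors lose 28% to 30%, and normals truncated at 80 mg/dL lose 35% to 37%. Lognormals lose 48.3% at log-SD 0.5 and 63.0% at log-SD 0.8. These floors apply at screening; baseline averages two values, so the true lower edge would be softer.

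**Power.** Φ(nc − 1.96) + Φ(−nc − 1.96), with nc = b / 3.73 for the continuous test and k × b / 7.45 for the split.

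| b | Continuous | Split, normal (loss) | Split, exponential (loss) |
|---|---|---|---|
| 2 | 8.4% | 7.1% (1.2) | 6.6% (1.8) |
| 4 | 18.9% | 13.7% (5.2) | 11.5% (7.3) |
| 6 | 36.3% | 25.0% (11.3) | 20.0% (16.3) |
| 8 | 57.4% | 40.2% (17.2) | 31.9% (25.5) |
| 10 | 76.5% | 57.2% (19.3) | 46.0% (30.5) |

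For a uniform baseline the loss is 0.9 points at b = 2 and 12.3 points at b = 10.

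**The reverse case.** Suppose the effect steps by 15 points at the median. The split has nc = 15 / 7.45 = 2.01 and 52% power. The linear test keeps only 64% (normal) or 48% (exponential) of that information, giving 36% or 29%.

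**Degrees of freedom.** The continuous figures are for a one-degree-of-freedom contrast. A joint three-degree-of-freedom test over weeks 8, 10 and 12 at the same noncentrality, (b / 3.73)², gives 24% at b = 6 and 41% at b = 8. The normal-case split gives 25% and 40%, so a joint test would remove the gain.

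**The case against.** The case against making much of this is substantial.

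- **The LDL-C split is prespecified in the protocol.** No objective or hypothesis concerns effect modification, and the rationale in Protocol 2.3 leads to recruitment criteria rather than to an estimand. The subgroup tests are supportive and lie outside the multiplicity procedure. This stands and limits the weight of the point.
- **The cardiovascular-risk half of the rationale is already covered** by stratification and by a subgroup whose strata have different LDL-C floors. This stands, although it does not describe a trend in LDL-C itself.
- **Large slopes are needed for a large loss.** At 10 points per SD, the effect would swing by 40 points between −2 and +2 SD, as much as the whole assumed effect. At 2 to 4 points per SD the gain is only 1 to 7 points, and neither test is informative. This stands.
- **A linear test can lose to the split**, as the step example shows. This is why the continuous analysis should be added beside the split and not replace it.

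A reader might go further in four ways, none of which the documents support. One is to treat a single loss range as a property of this plan; no baseline distribution or interaction size is given. Another is to extend the design-aim argument to PCSK9 and triglycerides; Protocol 2.3 names only cardiovascular risk and LDL-C. A third is to infer that the covariate-adjusted models use dichotomised values; SAP 9.5.1.2 does not say so. The last is to assume that a non-significant split will be reported as consistency; the SAP plans to estimate the differences as well as test them.

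What survives is narrower: no planned analysis describes how the effect varies along the LDL-C scale, although the values needed are already derived.

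**Conclusion.** The point holds as a modest improvement for baseline LDL-C. The stated rationale concerns the effect across LDL-C levels, and the only planned test of that is a median split. Under a roughly linear trend this loses about 25% to a little over 60% of the information over the shapes tried. The power loss runs from about 1 point at 2 points per SD to 19 (normal) or 31 (exponential) points at 10 points per SD. These figures rest on an assumed slope, an assumed baseline shape, a linear trend, and the plan's SD and dropout; a step near the median would reverse the advantage. For PCSK9 and triglycerides the argument is efficiency alone. The primary conclusion and type I error control are not affected.

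**What to change.** In SAP 9.5.1.2, keep the median-split subgroup analysis and add a prespecified supportive analysis of continuous baseline LDL-C within each dose frequency:

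- Add baseline, baseline-by-visit, treatment-by-baseline and treatment-by-baseline-by-visit terms to the repeated-measures model.
- Test the treatment-by-baseline slope as a one-degree-of-freedom contrast for each co-primary endpoint: at week 12, and as the mean of weeks 10 and 12.
- Report the treatment difference with 95% confidence interval at fixed LDL-C values, for example 80, 100, 130 and 160 mg/dL.
- Check linearity with a quadratic or spline term.

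The same analysis for PCSK9 and triglycerides is optional. The cost is a few sentences in the SAP and one extra supportive model, with no new data. The downside is a linearity assumption, which the curvature check and the retained split both help to examine.

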### **9.5.2 Analyses of Secondary Efficacy Endpoint(s)**

The statistical model and testing of the tier 1 secondary efficacy endpoints as described in estimands supporting the secondary objectives, will be similar to the primary analysis of the co-primary estimands. The secondary estimands of achievement of target LDL-C < 70 mg/dL and LDL-C response of ≥ 50% reduction from baseline will be analyzed using the Cochran-Mantel Haenszel (CMH) test adjusted by the stratification factor.

Analyses of the tier 2 secondary efficacy estimands will use the same analysis model as the tier 1 estimands, Refer to [Section 9.1](#) and [Figure 9-1](#) for multiplicity adjustment for multiple tier 1 and tier 2 secondary endpoints.

### **9.5.3 Analyses of Exploratory Efficacy Endpoint(s)**

Exploratory endpoints related to lipid parameters and PCSK9 will be summarized by randomized treatment group and by scheduled visit using descriptive statistics. Figures will be provided for change from baseline and percent change from baseline analyses.

Achievement of target LDL-C < 55 mg/dL and < 40 mg/dL will be analyzed using the Cochran-Mantel Haenszel (CMH) test adjusted by the stratification factor.

A shift table for hsCRP will be provided, for levels at baseline to maximum post-baseline value (<1, 1-3, >3 mg/L), by treatment group.

## **9.6 Safety Analyses**

### **9.6.1 Adverse Events**

The Medical Dictionary for Regulatory Activities (MedDRA) version 22.0 or later will be used to code all events categorized as adverse events (AEs) to a system organ class and a preferred term. Severity of AEs will be graded using the CTCAE and recorded on the eCRF. All treatment-emergent adverse event tables will be summarized by actual treatment group. Treatment-emergent adverse events are events with an onset after the administration of the first dose of IP as defined in [Section 5.3](#).

Subject incidence of all treatment-emergent AEs, serious AEs, AEs leading to withdrawal of investigational product, and fatal AEs will be tabulated by system organ class, high level term, and preferred term in descending order of frequency.

Summaries of treatment-emergent and serious AEs occurring in at least 1% of the subjects by preferred term in any treatment arm will be provided in descending order of frequency.

**All the summary of treatment-emergent adverse event/serious adverse event mentioned above will also include those reported as Disease Related Events (DRE).** Subject incidence of DREs will be summarized **separately** by system organ class and preferred term for all treatment-emergent DREs and fatal DREs **as well**.

Subject incidence of treatment-emergent adverse events related to a device will be tabulated by preferred term in descending order of frequency by treatment group.

Subject incidence of treatment-emergent adverse events associated with injectable protein therapies will be summarized by category and preferred term:

- Injection site reactions
- Hypersensitivity or allergic reactions

#### **9.6.2            Laboratory Test Results**

Descriptive statistics will be provided for actual values and changes from baseline in select laboratory parameters at each protocol-specified scheduled visit. Laboratory analytes are provided in the protocol Table 2. Lab shift tables using the CTCAE grading scale v4.03 or later will be used for the select analytes of interest, when applicable.

In addition, CK and liver function test (LFT) abnormalities will be assessed by the incidence overall and by visits of the following categories:

- CK > 5 x ULN
- CK > 10 x ULN
- ALT or AST > 3 x ULN
- ALT or AST > 5 x ULN
- Total bilirubin > 2 x ULN
- (ALT or AST > 3 x ULN) and Total bilirubin > 2 x ULN and Alkaline Phosphatase < 2 x ULN

#### **9.6.3            Vital Signs**

Systolic and diastolic blood pressures and heart rate will be summarized for each treatment group using descriptive statistics at each scheduled visit.

#### 9.6.4 Antibody Formation

The incidence and percentage of subjects who develop anti-evolocumab antibodies (binding and if positive, neutralizing) at any time, will be tabulated.

#### 9.6.5 Exposure to Investigational Product

Descriptive statistics will be produced to describe the exposure to investigational product by treatment group.

#### 9.6.6 Exposure to Other Protocol-required Therapy

The number and proportion of subjects receiving selected lipid regulating medications captured on the “**Other Protocol Required Therapy – [Statin (Lipid Lowering Therapy)]**” eCRF will be summarized by **preferred term or category for each treatment group as coded by the World Health Organization Drug (WHO DRUG) dictionary**. Summaries will be provided for baseline use and use after Study Day 1. The subject incidence of changes in lipid regulating medications during the treatment period will also be provided by treatment group.

### 10. Changes From Protocol-specified Analyses

**Eighteen subjects who were enrolled in the study will be excluded from all analyses (both efficacy and safety) because they would require additional Human Genetic Resource Administration office of China (HGRAC) approvals, as follows:**

- **According to the Administrative Regulations on Human Genetic Resources of the People's Republic of China, effective on 01 July 2019, if a study screens 500 Chinese subjects, the study must complete the HGRAC sample collection application. Thirteen subjects in Study 20150172 were enrolled after screening had reached 500; therefore, these 13 subjects will be excluded from the analyses.**
- **Under this same regulation, foreign-invested hospitals cannot participate in this application. Suzhou Kowloon Hospital, which enrolled 5 subjects in Study 20150172, is a Hong Kong-invested hospital, according to Implementation Regulations for Foreign Investment Law of P.R. China: “Investments in Mainland China by investors from Hong Kong Special Administrative Region shall be handled with reference to the Foreign Investment Law”. [REDACTED], the 5 subjects enrolled at this site [REDACTED] [REDACTED] will be excluded from the analysis.**

---

**Appendix A. Reference Values/Toxicity Grades**

Refer to the NCI Common Terminology Criteria for AEs (CTCAE) for AEs and lab shift grading and information. The CTCAE is available at the following link:

<http://evs.nci.nih.gov/ftp1/CTCAE/About.html>

## Appendix B. Lipid-lowering Background Therapy

### Lipid Modifying Background Therapy Intensity

(Group A) Intensive statin usage	Subject has at least one of the following recorded for the last 4 weeks prior to screening: 

• Atorvastatin <math>\geq</math> 40 mg QD

• Rosuvastatin <math>\geq</math> 20 mg QD

• Simvastatin <math>\geq</math> 80 mg QD (note that simvastatin 80 mg QD is not approved in some countries e.g., the United States)

• Any statin QD plus ezetimibe

(Group B) Non-intensive statin usage	Subject has been taking any dose of a statin at least weekly for the last 4 weeks prior to screening and is not included in Group A
(Group C) No statin	Subject is not included in Group A or Group B

Note:

 Statin includes atorvastatin, fluvastatin, lovastatin, pitavastatin, pravastatin, rosuvastatin and simvastatin.

### Appendix C. Framingham Risk Score

The method to calculate Framingham Risk Score is described below.

The  $\beta$  coefficients given in the two tables below are used to compute a linear function. The latter is corrected for the averages of the participants' risk factors (mean) from the Framingham study, and the subsequent result is exponentiated and used to calculate a 10-year probability of HCHD after insertion into a survival function ([Wilson et al](#)).

The calculation is different for men and women and uses the following coefficients  $\beta_i$ , where  $i$  represent each of the independent variables. The values below are from the Framingham heart study (<http://www.framinghamheartstudy.org/risk/hrdcoronary.html>).

$t\_chol$  = total cholesterol,  $hdl$  = HDL-C,  $sbp$  = systolic blood pressure,  $trt\_htn$  = treatment for hypertension (if  $sbp > 120$ ),  $smoker$  = current smoker

Men			Women		
Independent variable	Coefficient $\beta_i$	mean	Independent variable	Coefficient $\beta_i$	mean
ln(age)	52.00961	3.8926095	ln(age)	31.764001	3.9213204
ln(t_chol)	20.014077	5.3441475	ln(t_chol)	22.465206	5.3628984
ln(hdl)	-0.905964	3.7731132	ln(hdl)	-1.187731	4.0146369
ln(sbp)	1.305784	4.8618212	ln(sbp)	2.552905	4.8376494
trt_htn (spb>120)	0.241549	0.1180474	trt_htn (spb>120)	0.420251	0.142802
smoker	12.096316	0.335602	smoker	13.07543	0.3236202
ln(age)* ln(t_chol)	-4.605038	20.8111562	ln(age)* ln(t_chol)	-5.060998	21.0557746
ln(age)*smoke r 	-2.84367	1.2890301	ln(age)*smok er 	-2.996945	1.2519882
ln(age)*ln(age )	-2.93323	15.2144965			
 if age>70 then ln(70)*smoker			 if age>78 then ln(78)*smoker		

The steps to determine the FRS is the same for men and women.

## Men

For each subject:

1. Calculate  $L_{men} = \beta_{ln(age)} * ln(age) + \beta_{ln(t\_chol)} * ln(t\_chol) + \beta_{ln(hdl)} * ln(hdl) + \beta_{ln(sbp)} * ln(sbp) + \beta_{trt\_htn} * (if\ trt\_htn) + \beta_{smoker} * (if\ smoker) + \beta_{ln(age)*ln(t\_chol)} * ln(age) * ln(t\_chol) + \beta_{ln(age)*smoker} * ln(age) * (if\ smoker) + \beta_{ln(age)*ln(age)} * ln(age) * ln(age)$
2. Calculate  $A_{men} = L_{men} - 172.300168$  (note: the value of 172.300168 was derived based on the mean columns in above table)
3. Calculate  $B_{men} = \exp(A_{men})$
4. Calculate  $P_{men} = 1 - 0.9402^B_{men}$
5.  $FRS_{men} = P_{men} * 100$  (rounded to nearest integer)

## Women

For each subject:

1. Calculate  $L_{women} = \beta_{ln(age)} * ln(age) + \beta_{ln(t\_chol)} * ln(t\_chol) + \beta_{ln(hdl)} * ln(hdl) + \beta_{ln(sbp)} * ln(sbp) + \beta_{trt\_htn} * (if\ trt\_htn) + \beta_{smoker} * (if\ smoker) + \beta_{ln(age)*ln(t\_chol)} * ln(age) * ln(t\_chol) + \beta_{ln(age)*smoker} * ln(age) * (if\ smoker)$
2. Calculate  $A_{women} = L_{women} - 146.5933061$  (note: the value of 146.5933061 was derived based on the mean columns in above table)
3. Calculate  $B_{women} = \exp(A_{women})$
4. Calculate  $P_{women} = 1 - 0.98767^B_{women}$
5.  $FRS_{women} = P_{women} * 100$  (rounded to nearest integer)

## Notes

- For men, if subject is > age 70, then use  $ln(70)*smoker$
- For women, if subject is > age 78, then use  $ln(78)*smoker$
- For dichotomous variables  $trt\_htn$  and  $smoker$  use 1/0 to represent yes/no respectively
  - If a subject has  $sbp \leq 120$  mmHg, then  $trt\_htn$  is no

Calculated scores should match the interactive calculator

<http://hp2010.nhlbihin.net/atpiii/calculator.asp?usertype=prof>

